3.2 Ineligibility Criteria

- 3.2.1 Evidence of distant metastases.
- 3.2.2 Absence of macroscopic disease after upfront surgery, i.e. TxNx and TxN0. TxN+ and T1-3Nx are eligible if the T/N stage categories meet the criteria of 3.1.1
- 3.2.3 Previous irradiation for head and neck tumor; concurrent chemotherapy other than the treatment per protocol; previous chemotherapy \leq 3 months from start of RT.
- 3.2.4 Active untreated infection.
- 3.2.5 Major medical or psychiatric illness, which in the investigators' opinion would interfere with either completion of therapy and follow-up or with full and complete understanding of the risks and potential complications of the therapy.
- 3.2.6 Use of amifostine or pilocarpine before and during radiotherapy is not allowed.
- 3.2.7 Serum creatinine >1.3 or ULN, CCL < 60 cc/min, Peripheral neuropathy > grade 1, and/or frequency hearing loss that interferes with activities of daily living are contraindications to cisplatin but not to carboplatin (6.2.4).
- 3.2.8 Patients with > 10 pack years of smoking history and/or currently a smoker at the time of treatment.

4 PRETREATMENT EVALUATIONS

- 4.1 Each patient must have completed the following studies prior to irradiation:
 - 4.1.1 Complete history and physical exam including weight and performance status.

4.1.2 Complete dental evaluation. Any required dental extractions must be made and fluoride prophylaxis instituted prior to radiotherapy.

4.1.3 Speech pathology evaluation including instrumental swallowing assessment or clinical assessment of swallowing and administration of pretreatment swallowing and trismus exercises (*This assessment is a standard of care assessment for this patient population). Completion of pretreatment MD Anderson Dysphagia Inventory (MDADI) and Montreal Cognitive Assessment (MCA). Speech therapy evaluation has to take place before commencement of treatment.

4.1.4 Nutritional evaluation to be conducted within the first week of starting (chemo)radiation therapy.

4.1.5 Completion of the following laboratory studies: CBC with diff. and platelets, Metabolic Panel to include- sodium, potassium, glucose, calcium, magnesium, BUN, serum creatinine, total protein, albumin, alkaline phosphatase, total bilirubin, AST, ALT, and a creatinine clearance)

4.1.6 Completion of the following radiologic studies: CT of head and neck with < 3 mm contiguous slices in immobilization system (*with contrast, unless contraindicated*); whole body PET/CT (integration of both high resolution CT with contrast and dedicated PET acquisition through the head and neck are strongly suggested); MRI of head and neck with gadolinium including T1 and T2 weighted sequences in at least 2 different planes strongly suggested for primary tumors of the base of tongue (*optional-see 5.1.2*).

4.1.7 Audiogram to be conducted before or within the first week of starting therapy (*if inner ear is to be irradiated at mean dose ≥ 40 Gy*).

5 RADIATION THERAPY

5.1 Treatment Planning, Imaging and Localization Requirements

5.1.1 The immobilization device is a thermoplastic mask that covers both face and shoulders. A mouth piece is also indicated for all patients but those edentulous.

5.1.2 Treatment planning CT scans will be performed with the patient in the treatment position. I.V. contrast at the time of simulation is also recommended. A planning MRI scan is optional.

5.1.3 All tissues to be irradiated must be included in the CT scan. CT scan thickness should be 0.3 cm or less through the region that contains the primary target volumes. The regions above and below the target volume may be scanned with slice thickness up to 0.5 cm. MRI and PET/CT scans may be included to assist in definition of target volumes.

5.1.4 The GTV, CTV and PTV and normal tissues will be outlined on all CT slices in which the structures exist.

5.1.5 Image Guidance for IGRT: Daily image guidance of IMRT will be achieved using Linear-accelerator mounted MV cone beam CT images.

The procedure to register treatment day imaging dataset with the reference dataset will comply with the following recommendations:

- Region-of-Interest (ROI) or “clip box” for fusion is set to encompass the high dose PTV and adjacent spinal cord; if the supraclavicular region is a part of the target volume the ROI should extend to the C6 level;

- Automatic (based on bony anatomy) registration will be used; the result of the fusion will be visually checked for the alignment of the bony anatomy, such as vertebral bodies and applicable soft tissue structures (e.g., optic nerves and/or optic chiasm).

Following the registration, the translational corrections will be applied to the treatment couch. If all the variances are less than 2.0 mm, the treatment will proceed without correction (however, the physician/team may elect to perform adjustments even for a variance < 2.0 mm). If one or more corrections are 2.0-5 mm, adjustment is necessary prior to treatment; however, re-imaging is not mandatory. If one or more of the corrections are larger than 5 mm, the imaging must be repeated in addition to performing table/positioning adjustments.

5.1.6 Management of Radiation Dose to the Patient from IGRT

The estimates of patient doses per imaging study for various imaging systems vary considerably. The doses from helical MV CT scan on a tomotherapy unit were estimated to be in range from 1 to 3 cGy for head and neck studies, similar to doses reported for kV cone beam CT on Elekta Synergy machine. Thus, the doses for 3D imaging systems are in the range from 1 to 3 cGy for head and neck imaging and can contribute from 0.5 to 1.5% to the daily dose of 2.0 Gy. These are small enough dose contributions that if there is only one or two imaging study done per treatment session, the dose does not need to be incorporated into treatment planning and is not expected to have any clinical relevance to the patient.

5.2 Volume and ICRU Reference Point Definitions

The definition of volumes will be in accordance with the 1993 ICRU Report #50: Prescribing, Recording and Reporting Photon Beam Therapy.

5.2.1 *The Gross Tumor Volume (GTV)* is defined as all known gross disease determined from CT, clinical information, endoscopic findings and MRI in the case of tumors treated after biopsy alone.

5.2.2 *The Clinical Target Volumes (CTV)* is defined as the GTV plus areas considered to contain potential microscopic disease, delineated by the treating physician. The margin between the each GTV and its CTV will be typically 1-2 cm, with a minimum of 5 mm except in those areas where the GTV is immediately adjacent to structures known to be uninvolved. In postoperative cases, The CTV includes the operative bed and margins according to an assessment of the risk of subclinical disease.

The Planning Target Volume (PTV) will provide a margin around each CTV (*i.e. both the primary tumor and the lymph nodes containing clinical or radiographic evidence of metastases*) to compensate for the uncertainties of treatment set up and tissue deformation. A minimum of 5 mm around the CTV will be required in all directions to define each respective PTV in the setting of IGRT.

5.3 Target Definition

5.3.1 *Targets* are defined as follows: CTV1 or high dose volume that encompasses the GTV with a margin; in case there is no GTV available (i.e. after tonsillectomy) CTV1 encompasses the tumor bed or where the tumor was before surgery; CTV2, that typically includes the tissue around the gross tumor volume and/or the neck nodal stations that have high (>15%) risk of cancer involvement and/or lymph nodes that look suspicious on imaging; CTV3 includes contralateral lymph nodal stations and lower neck lymph nodal stations which have relatively lower risk (5-15%) of cancer involvement and do not look suspicious at imaging.

5.3.2 Positive lymph nodes are defined as those that meet any of the following criteria on CT: maximum axial diameter > 1cm (>5 mm if retropharyngeal); focal hypoattenuation within the node suggesting necrosis; irregular enhancement pattern; presence of extracapsular penetration as judged by 21peculated margins. Suspicious are those that measure between 7-9 mm in greatest axial dimension in neck levels III through IV; have a rounded appearance defined as a width to length ratio greater than 0.5; lack fatty hilum.

5.3.3 Lymph node stations or levels in the neck follow the surgical nomenclature. A station is considered positive if contains positive lymph nodes. However, in this case, only the positive lymph node(s) and not the whole station is (are) contoured as GTV. Moreover, expansion from GTV to CTV1 does not imply that the whole level will be part of CTV1.

5.3.4 The following (entire) lymph nodal stations are considered at high (>15%) risk of containing microscopic disease when negative/normal on clinical exam and imaging: levels II and III ipsilateral to the site of a positive lymph node in the neck. The entire level is drawn as CTV2⁴².

5.3.5 For lymph node stations different from ipsilateral levels II and III (5.3.5) only the suspicious finding and not the whole level has to be contoured as CTV2;

5.3.6 The following levels are routinely included in CTV3: level IB ipsilateral to neck disease; bilateral levels II, III, IV and V. Controlateral level IB is routinely excluded from any target volume. In the rare case that level IB has a positive or suspicious node, level IB becomes part of the appropriate target volume even in absence of positive level II nodes.

5.3.7 The anterior extent of the contour of level IB when included in CTV3 will stop at the anterior extent of the submandibular gland and therefore exclude the triangular fat space lateral to the deep extrinsic muscles of the tongue as shown elsewhere⁴².

5.3.8 Retropharyngeal nodes on both sides are routinely included in CTV3 from C1 to the bottom of C2

5.4 Organ At Risk (OAR) Definitions

Several organs at risk will be contoured on each patient planning CT as follows. In order to facilitate the spelling, a script will be run from Pinnacle to generate the regions of interest. OAR's are: mandible, brain, brainstem, cord, submandibular glands, thyroid gland, parotid glands, upper gastrointestinal mucosa⁴⁷, larynx⁴⁵, masticatory spaces, upper, middle and inferior constrictor muscles, cricopharyngeous muscle, esophagus, brachial plexuses, temporomandibular joints (TMJ), inner ears, internal, external and common carotid arteries. Paired organs will be divided into those on the dominant side of disease (dominant) and those on the opposite side (contralateral). An atlas on how to contour each structure is available at the web site of the University of Texas Medical Branch, <http://www.utmb.edu/radoncology/oar.htm> For planning purposes, the cord is expanded by 4 mm.

5.5 PTV and subPTV generation

Each CTV is expanded 5 mm isotropically to generate corresponding PTV's, PTV1, 2 and 3. Each PTV is further adjusted to come off the skin, by excluding the part that is within 3 mm to skin surface (PTV= CTV + 5mm – (skin -3mm)).

In order to achieve dose de-escalation on parts of the PTV (subPTV), each PTV is further divided into subPTV's whose prescription dose is as follows in table 6.

Table 6

Main PTV	SubPTV	Note	Px D (Gy)	Nomenclature
PTV1	overPTV1	Part of PTV1 that overlaps with larynx for edema+8 mm, superior constrictor m+8 mm, mandible + 8 mm, parotids, masticatory mm, esophagus, mid/low constrictor mm	63	PTV63
	truePTV1	Rest of PTV1	70	PTV70
PTV2	None		63	PTV63
PTV3	overPTV3	Part of PTV3 that overlaps with larynx for edema+8 mm, sup/mid/low constrictor mm+8 mm, parotids+8 mm, masticatory mm+8 mm, esophagus+8 mm	50.75	PTV50.75
	lowPTV3	Part of PTV3 that covers ipsilateral (to neck disease if present) level IV (and level III is negative) and/or contralateral (to neck disease or both heminecks if no neck disease is present) levels III and IV; if disease is present on both sides, each side is treated as ipsilateral one	50.75	PTV50.75
	truePTV3	Rest of PTV3 (or without lowPTV3 and overPTV3)	58.1	PTV58.1

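### The dose-reduction rule for level IV (Table 6, lowPTV3; section 1.5 items 2 to 4) never tests level IV itself, so the rest of a level IV holding a suspicious or positive node can be prescribed 50.75 Gy instead of 58.1 Gy

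*Combined protocol and SAP*

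**What the plan says.** **The reduction rule.** In section 5.5, Table 6 defines lowPTV3 (50.75 Gy) by two clauses.

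- The ipsilateral clause reads "Part of PTV3 that covers ipsilateral (to neck disease if present) level IV (and level III is negative").
- The second clause adds contralateral levels III and IV, or those levels in both heminecks when there is no neck disease. It prints no nodal condition. If there is disease on both sides, each side follows the ipsilateral clause.

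Section 1.5 gives the same scheme in prose. Item 2 lowers ipsilateral level IV if level III is uninvolved. Item 3 lowers contralateral levels III and IV if contralateral level II is negative. Item 4 lowers contralateral level IV if contralateral level III is negative, whatever the status of level II. PTV3 tissue outside lowPTV3 and outside the organ-at-risk overlap (overPTV3) is truePTV3, at 58.1 Gy.

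**The contouring rules (section 5.3).**

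- 5.3.2 defines suspicious nodes separately from positive ones: "Suspicious are those that measure between 7-9 mm in greatest axial dimension in neck levels III through IV", with shape and fatty-hilum criteria as well.
- 5.3.3: "A station is considered positive if contains positive lymph nodes". Only the positive node is GTV, and "expansion from GTV to CTV1 does not imply that the whole level will be part of CTV1".
- 5.3.5, for stations other than ipsilateral levels II and III: "only the suspicious finding and not the whole level has to be contoured as CTV2".
- 5.3.6 routinely places "bilateral levels II, III, IV and V" in CTV3. Its only exception for a positive or suspicious node concerns level IB.
- 5.3.1 describes CTV3 as stations "which have relatively lower risk (5-15%) of cancer involvement and do not look suspicious at imaging", and says that CTV2 "typically includes the tissue around the gross tumor volume".

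**The concern.** A rule that lowers the dose to a nodal level should ask whether that level looks involved. This one asks about level III or level II, or prints no condition. The size criterion in 5.3.2 is written for levels III through IV, so the protocol expects suspicious findings in the level that it de-escalates.

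The prescribed dose to part of one level is at stake, in a de-escalation trial with locoregional control as a primary endpoint. The reduced dose is below the lowest level of the institution's usual practice (58.1 Gy, section 5.6). Quality assurance would not catch it: section 5.10.1 scores each PTV, including PTV50.75, against its own prescription. Under the Schema, T1-2 patients with N0-1 or N2a below 5 cm receive IMRT alone, so some affected patients could have no concurrent chemotherapy.

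**Working it through.** **1. Reproduce the plan's figures.** Inputs from Table 4 and its footnotes: 35 fractions in 47 days, α/β = 10 Gy, α = 0.35 per Gy, Tk = 21 days, Tp = 5 days.

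BED10 = D(1 + d/10) − ln 2 × (47 − 21)/(0.35 × 5). The time term is 10.30 Gy.

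| Dose level | D(1 + d/10) | BED10 | Table 4 |
|---|---|---|---|
| 58.1 Gy at 1.66 Gy | 67.74 | 57.45 | 57.4 |
| 50.75 Gy at 1.45 Gy | 58.11 | 47.81 | 47.8 |

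Both reproduce.

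**2. Size of the difference.** Physical dose: 58.1 − 50.75 = 7.35 Gy. BED10: 57.45 − 47.81 = 9.64 Gy, and 9.64/57.45 is about 17%. In 2-Gy equivalents Table 4 gives about 52 against about 42 Gy.

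**3. Trace a suspicious level IV node (7-9 mm), level III negative.**

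- 5.3.2: the node is suspicious, not positive.
- 5.3.5: only the node becomes CTV2. With the 5 mm expansion of section 5.5, PTV2 measures 0.7 + 2 × 0.5 = 1.7 cm to 0.9 + 2 × 0.5 = 1.9 cm, at 63 Gy.
- 5.3.6: the rest of level IV stays in CTV3.
- Table 6: that remainder is lowPTV3, at 50.75 Gy. If this is the only nodal finding and the neck therefore counts as free of disease, the second clause applies and gives the same dose with no condition to check.

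**4. Trace a positive level IV node, level III negative.**

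- 5.3.3: only the node is GTV, and CTV1 need not cover the level.
- 5.3.4: negative levels II and III on that side become CTV2, at 63 Gy.
- 5.3.6 and Table 6: any level IV outside the expansions can be 50.75 Gy.
- Section 5.2.2 sets the GTV-to-CTV margin at 5 mm minimum and 1-2 cm typically. For a 1 cm node, PTV1 is 1 + 2 × (0.5 + 0.5) = 3 cm at the minimum margin. At the typical margins it is 1 + 2 × (1 + 0.5) = 4 cm to 1 + 2 × (2 + 0.5) = 6 cm. Little or nothing of level IV may be left, so the suspicious-node case is the clearer one.

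**5. Compare with a level IV that looks clear.** If ipsilateral level III is positive and level IV is negative, the ipsilateral condition fails and level IV is truePTV3 at 58.1 Gy. So a level IV with no finding can receive more than the rest of a level IV that contains one.

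**6. Does 5.3.1 settle it?** Its description would exclude a suspicious-looking station from CTV3. But 5.3.5 sends only the finding to CTV2. Applied literally together, the two would leave the rest of the level in no target volume. 5.3.6 avoids that by keeping level IV in CTV3, which returns it to the lowPTV3 rule.

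**The case against.** The strongest defence is that lowPTV3 is by definition part of PTV3, and 5.3.1 reserves CTV3 for stations at 5-15% risk that look clear. Tissue above 15% risk belongs in CTV2 at 63 Gy, and section 5.2.2 leaves delineation to the treating physician. Read this way, the low dose is avoidable. This stands in part: the text permits the low dose but does not force it. It does not resolve the conflict, because 5.3.5 and 5.3.6 are the specific contouring rules and the positive-or-suspicious exception is written for level IB alone.

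A second defence is that level-based reduction is the intervention under test and rests on a cited nodal-risk study. That supports reducing uninvolved levels. The documents do not say that it supports reducing a level with a finding in it.

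Item 2 of section 1.5 also refers to 5.3.2 for its criteria of involvement, which helps to define a negative level. It still applies them to level III, not level IV.

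A reader might go further and compare the 42 Gy equivalent with Table 3: 46 Gy by radiotherapy alone, or about 50 Gy with chemotherapy for high-risk areas, suggesting shortfalls of 4 and 8 Gy. The documents do not support this. They assign the remainder no risk, and if it were judged above 15%, 5.3.1 would send it to CTV2. The 46 Gy also rests on D0 = 2.5 Gy, the top of Table 3's typical 1.5-2.5 Gy. At D0 = 42/(8 × 2.3) = 2.28 Gy or less, 42 Gy covers the same 8 logs. Table 3's low-risk figure with chemotherapy is about 40 Gy.

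**Conclusion.** The point holds as an incoherence in a stated dose rule. Both lowPTV3 clauses and section 1.5 items 2 to 4 can place the rest of a level IV holding a suspicious or positive node at 50.75 Gy, which is 7.35 Gy (BED10 about 9.6 Gy, or 17%) below the alternative of 58.1 Gy. The BED figures rest on Table 4's own parameters. Tissue in overPTV3 is at 50.75 Gy either way.

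Two further inferences should not be drawn. The node itself is not de-escalated to 50.75 Gy: a suspicious node lies in PTV2 and a positive one in PTV1. Nor can any loss of locoregional control be stated, because the documents give neither the frequency of this nodal pattern nor an effect on control. For the same reason it cannot be called rare or common.

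Severity is minor: a cheap improvement to the text.

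**What to change.** Keep the existing level II and level III conditions. Add to both lowPTV3 clauses in Table 6 and to section 1.5 items 2, 3 and 4: *and the level being reduced itself contains no positive or suspicious node (5.3.2)*. Item 3 and the second clause must be included; otherwise a suspicious level IV in a contralateral or node-negative neck would still be reduced. This wording also covers contralateral level III, which those two provisions lower together with level IV. It adds no bar on reducing level IV when only level III is suspicious.

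Then state in 5.3.1 and 5.3.6 that the remainder of such a level stays in CTV3 as truePTV3 at 58.1 Gy, apart from overPTV3, unless the physician judges it high risk and assigns it to CTV2 at 63 Gy. This removes the conflict between those sections.

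The cost is a short text amendment, with no extra patients, visits or procedures and no change to the sample size of 60. The downside is somewhat less reduced-dose volume in affected patients. Their number is unknown, and the shape and fatty-hilum criteria in 5.3.2 also count as suspicious.

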5.6 Dose prescription

The common practice of this institution for H&N cancer is to prescribe three dose levels, 70 Gy, 63 Gy and 58.1 Gy to primary tumor and whole neck (PTV1-3) in 35 fractions. The Px to each PTV is reported in table 6. Now we have 4 dose levels, 70, 63, 58.1 and 50.75 Gy. In cases after primary tumor surgery where there is no residual macroscopic disease left, the total dose to PTV1 can be reduced from 70 Gy to 68.25 Gy. In this case PTV68.25 is treated as PTV70 regarding overlap with the various OAR's.

5.7 Planning

5.6.1 A co-planar 9 beam whole field IMRT plan will be generated. The treatment plan used for each patient will be based on an analysis of the volumetric dose, including DVH analyses of the PTV and critical normal structures. An “inverse” planning using computerized optimization is used. The treatment aim will be the delivery of radiation to the PTVs and the exclusion of noninvolved tissue as feasible.

5.6.2 Dose Specification

5.6.2.1 The prescription dose is the isodose which encompasses at least 95% of the planning target volume (*PTV*). No more than 10% of any planning target volume (*PTV*) will receive >110% of its prescribed dose ($V_{10\%} \leq 110\%$). No more than 1% of any planning target volume (*PTV*) will receive <95% of its prescribed dose ($V_{95\%} > 99\%$). No more than 1% or 1 cc of the tissue outside the PTVs and any OAR (unspecified tissue) will receive >110% of the dose prescribed to PTV1.

5.6.2.1 The prescription dose to the PTV's and subPTV's is reported in table 5. Breaks in treatment should be minimized. Break in treatment time of more than 5 days will be considered a major variation.

5.6.2.2 The reported doses for each PTV shall include the prescription dose as well as the maximum point dose, % target volume receiving > 110% and >115% of its prescribed dose and the % target volume receiving < 95% of the prescribed dose, and the mean dose to the PTV.

5.6.2.3 The dose prescription is to be based on a dose distribution corrected for heterogeneities

5.6.3 Critical Normal Structures

DVHs must be generated for all critical normal structures and the unspecified tissues. Dose constraints to normal tissues (and PTV's) should be as per table 7.

Table 7.

Group	Region of interest		
1	Cord+4 mm	0.1 cc	Max dose 45 Gy
	Brainstem	0.1 cc	Max dose 54 Gy
	Brain	1 cc	Max dose 60 Gy
	Larynx for edema+8 mm-over2	Portion overlapping with PTV2	Max dose 63 Gy
	Larynx for edema+8 mm	Portion not overlapping with PTV2	Max dose 50.75 Gy
	Mandible+8 mm		Max dose 63 Gy
	Sup constrictor m+8 mm-over2	Portion overlapping with PTV2	Max dose 63 Gy
	Sup constrictor m+8 mm	Portion not overlapping with PTV2	Max dose 50.75 Gy
	Mid constrictor m – over2	Portion overlapping with PTV2	Max dose 63 Gy
	Mid constrict m+8 mm	Portion not overlapping with PTV2	Max dose 50.75 Gy
	Low constrictor m – over2	Portion overlapping with PTV2	Max dose 63 Gy
	Low constrict m+8 mm	Portion not overlapping with PTV2	Max dose 50.75 Gy
	Parotids – over2	Portion overlapping with PTV2	Max dose 63 Gy
	Parotids+8 mm – over3	Portion overlapping with PTV3	Max dose 50.75 Gy
	Masticatory mm – over2	Portion overlapping with PTV2	Max dose 63 Gy
	Masticatory mm+8 mm	Portion not overlapping with PTV2	Max dose 50.75 Gy
	Esophagus – over2	Portion overlapping with PTV2	Max dose 63 Gy
	Esophagus+8 mm – over3	Portion overlapping with PTV3	Max dose 50.75 Gy
Mucosa -1		V66.5 Gy<64.5 cc	
	Unspec. Tissue	1 cc	Max dose 77 Gy
2	overPTV1	Portion overlapping with OAR's (table 5)	V60 Gy >99%
	truePTV1	PTV1-overPTV1	V66.5 Gy >99%
	PTV2		V60 Gy >99%
	overPTV3	Portion overlapping with OAR's (table 5)	V48.2 >99%
	lowPTV3	Low/mid neck PTV3 (table 5)	V48.2 >99%
	truePTV3	PTV3-lowPTV3-overPTV3	V55.2 >99%
3	Mucosa -2	Portion not overlapping with any PTV	Max dose 30 Gy
	Parotids	At least one	V30<50% (whole DVH)

Brachial plexus		Max dose 60 Gy
Inner ears		Mean D <40 Gy
Esophagus-out	Portion outside PTV3+8 mm	Dmax 45 Gy

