5.6.4 Planning Priorities

The priorities in addressing the protocol aims and constraints will be in the following order:

- 1) Group 1 (table 6),
- 2) Group 2 (table 6),
- 3) Group 3 (table 6).

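### Table 7 caps five organ volumes at 50.75 Gy outside PTV2 without exempting PTV1, so the written limits contradict the PTV1 prescription wherever PTV1 extends beyond PTV2

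*Combined protocol and SAP*

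**What the plan says.** Table 7 (5.6.3) sorts planning limits into three groups. Group 1 holds the organ limits and Group 2 the target coverage. Section 5.6.4 says "The priorities in addressing the protocol aims and constraints will be in the following order" and lists Group 1, then Group 2, then Group 3. It locates the groups in Table 6, although they are in Table 7.

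In Group 1, five volumes have a 50.75 Gy maximum for the "Portion not overlapping with PTV2": larynx, superior constrictor, middle constrictor, low constrictor and masticatory muscles, each expanded by 8 mm. Companion rows allow 63 Gy where the organ overlaps PTV2. None of these rows mentions PTV1.

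Table 6 (5.5) splits PTV1 in two. The 63 Gy part, overPTV1, is defined as "Part of PTV1 that overlaps with larynx for edema+8 mm, superior constrictor m+8 mm, mandible + 8 mm", plus the overlap with parotids, masticatory muscles, esophagus and middle and low constrictors without a margin. The remainder, truePTV1, gets 70 Gy. Group 2 asks that more than 99% of overPTV1 receive 60 Gy and more than 99% of truePTV1 receive 66.5 Gy.

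Whether PTV2 contains PTV1 is left open. Section 5.3.1 says only that CTV2 "typically includes the tissue around the gross tumor volume" and/or certain nodal stations.

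**The concern.** A planner who meets a piece of PTV1 outside PTV2 but inside one of the five expanded volumes is given two limits that exclude each other. Read literally, the priority order decides against the target. Part of PTV1 would then be limited to the dose that Table 6 gives to overPTV3 and lowPTV3, whereas section 1.5 plans to lower PTV1 only to 60 Gy ED2. Locoregional control is a primary endpoint, and a failure in such a spot could not be cleanly attributed to the 63 Gy reduction under test.

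The target rules leave room for this. A retropharyngeal node above 5 mm counts as positive (5.3.2), and "only the positive lymph node(s) and not the whole station is (are) contoured as GTV" (5.3.3). For the station, "Retropharyngeal nodes on both sides are routinely included in CTV3 from C1 to the bottom of C2" (5.3.8). For stations other than ipsilateral levels II and III, "only the suspicious finding and not the whole level has to be contoured as CTV2" (5.3.5). No rule explicitly requires CTV2 around such a node, and its PTV1 may reach the expanded superior constrictor.

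**Working it through.** **Plan's own figures.** The Group 2 coverage doses are 95% of the Table 6 prescriptions:
- 0.95 × 70 = 66.5 (stated 66.5)
- 0.95 × 63 = 59.85 (stated 60)
- 0.95 × 58.1 = 55.2 (stated 55.2)
- 0.95 × 50.75 = 48.2 (stated 48.2)

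Tables 6 and 7 therefore agree on the targets. The mismatch is confined to the organ rows.

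**Cap against PTV1, where PTV1 lies outside PTV2**

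| Part of PTV1 | Prescription | Gap to prescription | Cap / prescription | Gap to Group 2 dose |
|---|---|---|---|---|
| overPTV1 (inside larynx + 8 mm, superior constrictor + 8 mm, middle/low constrictors, masticatory muscles) | 63 Gy | 63 − 50.75 = 12.25 Gy | 80.6% | 60 − 50.75 = 9.25 Gy |
| truePTV1 (8 mm rim of middle/low constrictors and masticatory muscles) | 70 Gy | 70 − 50.75 = 19.25 Gy | 72.5% | 66.5 − 50.75 = 15.75 Gy |

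The rim falls in truePTV1 because Table 6 takes those muscles without a margin, while the Table 7 caps add 8 mm. By Table 4, 50.75 Gy is about 42 Gy ED2 for tumor, against about 60 Gy for 63 Gy. Part of the affected tissue may be margin: with a 1–2 cm GTV-to-CTV margin (5.2.2) and 5 mm to PTV (5.5), the PTV1 edge typically lies 10 + 5 = 15 to 20 + 5 = 25 mm from the GTV.

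**Dependence on how PTV2 is read**
- PTV2 encloses PTV1: the 63 Gy rows match Table 6 and the rim is uncapped. No conflict.
- PTV2 stands for the PTV63 label, which Table 6 gives to both overPTV1 and PTV2: overPTV1 is cleared. Only truePTV1 in the 8 mm rim conflicts, and only where PTV2 does not cover it.
- PTV2 means PTV2 alone and PTV1 extends beyond it: both rows of the table apply.

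**Does the 110% rule settle nesting?** Section 5.6.2.1 lets at most 10% of any PTV exceed 110% of its dose. For PTV2 that is 1.10 × 63 = 69.3 Gy, and 70/63 = 111.1%. If 95% of truePTV1 receives 70 Gy, then 0.95 × share ≤ 0.10, so truePTV1 could fill at most about 10.5% of PTV2. That strains nesting. But the protocol also draws ipsilateral levels II–III as CTV2 (5.3.4) while putting bilateral levels II–V in CTV3 (5.3.6), and Table 7 forms truePTV3 without removing PTV1 or PTV2. The rule would be strained there too (70/58.1 = 120.5%), so it decides nothing.

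**Were the caps treated as hard?** Table 5 gives a superior constrictor mean of 67.3 Gy with a 3.7 Gy gain. Even if 67.3 is the reference plan, the proposed solution gives 67.3 − 3.7 = 63.6 Gy, a mean above the 63 Gy maximum.

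**The case against.** The strongest reply is that the authors meant PTV2 to enclose PTV1. The 63 Gy rows follow the overPTV1 list in Table 6, margins included, and PTV2 has no sub-volumes of its own, so those margins make sense only if the rows serve overPTV1. Nesting is therefore probably what was intended. What stands against this is only that the protocol does not say so, and 5.3.1 hedges.

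A reader might infer that the retropharyngeal node proves gross disease is held at 50.75 Gy. The documents do not support that. A positive node is GTV, and 5.3.1 can be read as placing CTV2 around any GTV. Section 5.3.5 limits how much of a level is drawn for a suspicious finding; it does not withdraw CTV2 from around gross disease. The node is a possible case, not a demonstration.

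Nor do the documents show underdosing in practice. Table 7 limits are worded as what should be met. Table 8 scores PTV coverage, with V95% below 95% a major variation. It does not score the 50.75 Gy caps, and its superior constrictor limits (V60 below 80%, V65 below 70%) would be pointless if a 63 Gy maximum were binding. Table 5 points the same way. All of this stands and keeps the point minor. It does not remove the contradiction: Table 8 can flag poor coverage but does not amend Table 7 or say which limit yields.

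**Conclusion.** Wrong as written, of minor severity. In any plan where PTV1 lies outside PTV2 within the five expanded volumes, the Group 1 cap contradicts Table 6 and Group 2 by 12.25 Gy (overPTV1) or 19.25 Gy (truePTV1 in the rim) against prescription, and the stated order favors the cap. The gap is zero wherever PTV2 encloses PTV1. If PTV2 is read as PTV63, only the 19.25 Gy case remains.

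These are gaps between written limits, not delivered doses. The documents do not say how often the geometry occurs, and actual underdosing of gross disease is not shown. Sample size and the statistical analysis are unaffected.

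**What to change.** 1. Table 7, the five 50.75 Gy rows: apply them to the portion outside both PTV1 and PTV2.
2. Table 7, the 63 Gy companion rows: apply them to the portion inside PTV1 or PTV2, keeping the margins already in Table 7. The overPTV1 coverage dose (60 Gy) then lies below its 63 Gy limit, and truePTV1 in the 8 mm rim is no longer capped below 66.5 Gy.
3. Section 5.6.4: add that inside PTV1 the Table 6 prescription and Group 2 coverage take precedence over the 50.75 Gy caps, and point the group reference to Table 7.

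Stating instead that PTV2 contains PTV1 would also work, but PTV1 would then need exempting from PTV2's 110% limit in 5.6.2.1.

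The cost is a text amendment to one table and one paragraph, using doses already in Table 6, with no added patients, visits or procedures. The downside is slightly less organ sparing inside PTV1, which Table 6 never intended.
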